#### **9.3.2.6. *The change from Baseline to Day 28 of Treatment Period 6 in number of tender joints***

Both estimands, as well as the estimands where the ITT is replaced by the mITT, all randomized and PP sets, for this key secondary efficacy will be tested between each SEL-212 treatment group versus placebo using the mixed model for repeated measures (MMRM) with change in tender joints from baseline as dependent variable and treatment, period, treatment-by-period interaction, randomization stratum and baseline value of tender joints as fixed effect variables. The unstructured covariance structure will be used for the MMRM. The Least Square (LS) Mean difference between each SEL-212 and placebo treatments groups will be estimated on the treatment-by-visit interaction at TP6-Day 28 visit, along with its 97.5% confidence interval, and 2-sided p-values.

A sensitivity analysis will be performed for the main estimand: missing values of number of tender joints at Day 28 TP6 will be multiple imputed by using the regression and predictive mean matching (RPMM) method considering tophus status at baseline and treatment group. The change from baseline to Day 28 of TP6 in tender joints will be analyzed using an ANCOVA with treatment and randomization stratum as fixed effects and the baseline value of tender joints as covariate.

The number of tender joints at scheduled visits and the change from baseline will be summarized by treatment group and period on the ITT, mITT, all randomized and PP populations.

#### **9.3.2.7. *The change from Baseline to Day 28 of Treatment Period 6 in total score of the Health Assessment Questionnaire (HAQ-DI)***

Both estimands, as well as the estimands where the ITT is replaced by the mITT, all randomized and PP sets, for this key secondary efficacy will be tested between each SEL-212 treatment group versus placebo using MMRM with change in HAQ-DI total score as dependent variable and treatment, period, treatment-by-period interaction, randomization stratum and baseline value of HAQ-DI total score as fixed effect variables. The unstructured covariance structure will be used for the MMRM. LSMean difference between each SEL-212 and placebo treatments groups will be estimated on the treatment-by-visit interaction at TP6-Day 28 visit, along with its 97.5% confidence interval, and 2-sided p-values.

A sensitivity analysis will be performed for the main estimand: missing values of HAQ-DI total score at TP6-Day 28 will be multiple imputed by using the RPMM method considering tophus status at baseline and treatment group, and the change from baseline to Day 28 of TP6 in HAQ-DI total score will be analyzed using an ANCOVA with treatment and randomization stratum as fixed effects and the baseline value of HAQ-DI total score as covariate.

The HAQ-DI total score at scheduled visits and the change from baseline will be summarized by treatment group and period on the ITT, mITT, all randomized and PP populations.

The HAQ-DI, which includes the patient global assessment and pain scale, is an instrument that assesses fine movements of the upper extremity, locomotor activities of the lower extremity, and activities that involve both the upper and lower extremities. Standard scoring takes into account the use of aids and devices or assistance from another person. There are 20 items in 8 categories that represent a comprehensive set of

This document is confidential.

functional activities: dressing, rising, eating, walking, hygiene, reach, grip, and usual activities. The stem of each item assesses a patient's functional ability using their usual equipment during the past week. Each category contains at least 2 specific sub-category questions. For example, under the category "walking," patients are asked about their ability to walk outdoors on flat ground and to climb up 5 steps.

The HAQ-DI includes a patient global assessment of disease and a visual analog scale for pain assessment.

Eight (8) categories will be assessed by the HAQ-DI: 1) dressing and grooming, 2) arising, 3) eating, 4) walking, 5) hygiene, 6) reaching, 7) gripping, and 8) common daily activities. There are 2 or 3 questions for each section. Scoring within each section is on a 4-point Likert scale from 0 (without any difficulty) to 3 (unable to do). The score given to each section is the worst (highest) score within the section (ie, if one question is scored 1 and another 2, then the score for the section is 2). In addition, if an aid or device is used or if help is required from another individual, then the minimum score for that section is 2. If the section score is already 2 or more then no modification is made. The sum of the 8 scores of the 8 sections will be divided by 8 to obtain the HAQ-DI total score. In the event that one section is not completed by a patient then the summed score would be divided by 7. The HAQ-DI total score will be calculated if 6 or more sections are available, otherwise it will be defined as missing

#### **9.3.2.8. Gout Flare Incidence During Treatment Periods 1-6**

The gout flare incidence is defined as the total number of gout flares a patient experiences in respective time period divided by the length of observation of the patient in this time period. Both estimands, as well as the estimands where the ITT is replaced by the mITT, all randomized and PP sets, for this key secondary efficacy will be tested between each SEL-212 treatment group versus placebo using ANOVA model with incidence of gout flares as dependent variable and treatment and randomization stratum as fixed effect variables. Missing values of gout flare incidence by TP6-Day 28 will be multiple imputed by using the RPMM method considering tophus status at baseline and treatment group. The LSMean difference between each SEL-212 and placebo treatments groups will be provided along with its 97.5% confidence interval, and 2-sided p-values.

In a supportive analysis, for each defined estimand the comparison between each SEL-212 treatment group and placebo will be performed using MMRM with the dependent variable 'incidence of gout flares in the study (TP1-6)' and treatment, 3-month period (months 1-3 versus months 4-6), treatment-by-3-month period interaction and randomization stratum as fixed effects. The LSMean difference between each SEL-212 and placebo treatment groups will be presented for each 3-month period, along with its 97.5% confidence interval, and 2-sided p-values.

In a further supportive analysis, the total number of gout flares by TP6-Day 28 will be analyzed. Missing values of total number of gout flares by TP6-Day 28 will be multiple imputed by using the RPMM method considering tophus status at baseline and treatment group. The total number of gout flares will be analyzed using an ANOVA with treatment and randomization stratum as fixed effects.

A summary table of the incidence of gout flares during the study and stratified by 3 months period (month 1-3 and month 4-6 after start of study treatment) will be provided by treatment group on the ITT, mITT, all randomized and PP populations. Summary tables of the total number of gout flares during the study will be provided by treatment group and overall and additionally stratified by severity on the ITT, mITT, all randomized and PP populations. Summary tables of the number of gout flares during the first 3 months

This document is confidential.

(TP1-3) and the next three months (TP4-6) will be provided by treatment group in overall and additionally stratified by severity on the ITT, mITT all randomized and PP populations.

### **9.3.2.9. Gout Flare Incidence During Treatment Periods 1-3**

The gout flare incidence is defined as the total number of gout flares a patient experiences in respective time period divided by the length of observation of the patient in this time period. Both estimands, as well as the estimands where the ITT is replaced by the mITT, all randomized and PP sets, for this key secondary efficacy will be tested between each SEL-212 treatment group versus placebo using NOVA model with incidence of gout flares as dependent variable and treatment and randomization stratum as fixed effect variables. Missing values of gout flare incidence by TP3-Day 28 will be multiple imputed by using the RPMM method considering tophus status at baseline and treatment group. The LSMean difference between each SEL-212 and placebo treatments groups will be provided along with its 97.5% confidence interval, and 2-sided p-values.

In a supportive analysis, the total number of gout flares by TP3-Day 28 will be analyzed. Missing values of total number of gout flares by TP3-Day 28 will be multiple imputed by using the RPMM method considering tophus status at baseline and treatment group. The total number of gout flares will be analyzed using an ANOVA with treatment and randomization stratum as fixed effects.

### **9.3.3. Additional Secondary Efficacy Endpoints and Analyses**

- Percentage of patients who achieve and maintain reduction of sUA < 6 mg/dL for 100% of the time during TP6:

A frequency table of number and percentage of patients who achieve and maintain reduction of sUA < 6 mg/dL for 100% of the time during TP6 will be provided on the ITT population. Each SEL-212 treatment group will be compared versus placebo using the MH estimate and test for common risk difference considering the randomization stratum of tophus presence (yes/no) on the ITT population. In addition, 95% confidence intervals for treatment differences between each SEL-212 treatment group and placebo will be computed.

- Number with pre-dose sUA values < 6 mg/dL during TPs 2-6 for each patient:

A summary table of the mean number of TPs with pre-dose sUA values < 6 mg/dL during TP2 to TP6 will be provided by treatment group on the ITT population. Each SEL-212 treatment group will be compared versus placebo using ANCOVA model with the number of pre-dose values < 6 mg/dL during TPs 2-6 for each patient as dependent variable and treatment group as independent fixed effect variable. 95% confidence intervals for treatment differences between each SEL-212 treatment group and placebo will be presented.

- Anti-pegadricase and anti-uricase antibody formation and levels, pre-treatment for each treatment period in the SEL-212 active treatment arms during Treatment Periods 1-6:

Summary table of pre-treatment values of each variable will be provided by treatment period and by SEL-212 treatment group on the ITT population.

A descriptive summary table of D21 anti-pegadricase and anti-uricase antibody titers, D21 uricase activity values and D21 SUA values at each treatment period, stratified by treatment arm and whether or not the D21 SUA was above or less than or equal to the stopping rule level for that TP (i.e.  $\leq 1$  mg/dL in TP1 and  $\leq 6$  mg/dL in TPs 2-6).

This document is confidential.

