## **6. Estimands for Primary and Key Secondary Efficacy Endpoints**

### **6.1. Estimands are defined for the confirmatory analysis of efficacy in the double-blind treatment period. Estimands for Primary Efficacy**

The **main estimand** for the primary efficacy endpoint ‘percentage of patients who achieve and maintain reduction of sUA < 6 mg/dL for at least 80% of the time during Treatment Period 6 by Day 28’ is defined as follows:

- Population: Of all patients with gout refractory to conventional treatment defined by the study inclusion / exclusion criteria, the analysis population will include patients who were randomized to study treatment and who were dosed (ITT population)
- Variable: Binary variable indicating response status, whereby a responder is defined as a patient who has sUA < 6 mg/dL for at least 80% of the time during TP6.
- Population-level summary: Difference in the percentage of treatment responders of each SEL-212 treatment group versus placebo.
- Intercurrent events:
  - o Meeting the pre-defined treatment stopping criteria is considered as lack of efficacy and will be defined as treatment failures according to the composite strategy
  - o Premature stopping of study treatment due to treatment-related or non-treatment related AE, with the exception of a positive COVID-19 test result along with severe or critical symptoms of COVID-19, will be considered as treatment failure according to the composite strategy
  - o Premature stopping of study treatment due to a positive COVID-19 test result along with severe or critical symptoms of COVID-19 will be defined as treatment failures according to the composite strategy
  - o Death will be considered as treatment failure and will be treated according to the composite strategy
  - o Use of prohibited medication that lower sUA levels will be considered as treatment failure and will be treated according to the composite strategy
  - o All other intercurrent events (e.g. use of prohibited medication that do not lower sUA levels but are classified as a major protocol deviation) will be treated using the treatment policy strategy, i.e. the assessment of sUA in TP6 up to Day 28 will be used

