### **7.3. Missing Data**

Missing data will be imputed for the primary efficacy and key secondary efficacy variables as described in Section 9.

Missing or incomplete dates in safety data: In all listings, missing or incomplete dates will be left as they have been recorded. However, for calculation and sorting based on dates and for consideration in summary tables, the following method will be used: The most conservative approach will be systematically considered (i.e. if the onset date of an AE/concomitant medication is missing or incomplete, it is assumed to have occurred during the study treatment phase (i.e. a TEAE for AEs) except if the partial onset date indicates differently). A missing/incomplete date of medical history or disease diagnosis will be assumed to have occurred before any study treatment.

Missing TEAE relationship will be imputed by 'related'.

This document is confidential.

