## **9.2. Analyses of Primary Efficacy Estimands**

The statistical testing of each SEL-212 treatment group versus placebo in all four estimands will be performed using the Mantel-Haenszel (MH) estimate and test for common risk difference considering the randomization stratum of tophus presence (yes/no) with a two-sided type 1 error rate  $\alpha = 2.5\%$  to adjust for the two comparisons against placebo. Only the test results of the main estimand will be considered as confirmatory.

In addition, a logistic regression model will be fitted, with response as the outcome variable, tophus presence (yes/no) at baseline, treatment group included as covariates.

The analysis of all four estimands will be carried out based on the ITT population, and analyses on the main, second and third estimand will be performed, but the population will be changed to the mITT, the PP and the all randomized set, as opposed to the ITT.

For missing response evaluation data in TP6 (see also Section 9.1) values will be multiple imputed. The logistic method considering the tophus status at baseline and the treatment group will be applied for the multiple imputation.

For the main, second and fourth estimand of primary efficacy, sensitivity analysis will be performed using the tipping-point analysis for binary response, to investigate the sensitivity to departures from missing-at-random (MAR). For patients with missing response status, the underlying response probability will be varied systematically and comprehensively such that, should one exist, a tipping point can be identified where if

This document is confidential.

the probability of being a non-responder in the treatment group is higher than in the placebo group, the statistical significance switches from treatment effect p-value  $<0.025$  to treatment effect p-value  $\geq 0.025$ . For each arm, the following scenarios will be explored, where the true underlying response probability amongst those with missing response status will have the following probabilities:

0.01, 0.11, 0.21, 0.31, 0.41, 0.51, 0.61, 0.71, 0.81, 0.91, 0.99.

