#### 14.2.5.2. Table Conventions

- Units will be included where available
- If the categories of a parameter are ordered, then all categories between the maximum and minimum category are presented in the table, even if n=0 for all treatment groups in a given category that is between the minimum and maximum level for that parameter. For example, the frequency distribution for symptom severity would appear as:

Severity Rating	N
severe	0
moderate	8
mild	3

Where percentages are presented in these tables, zero percentages will not be presented and so counts of 0 will be presented as 0 and not as 0 (0%).

- If the categories are not ordered (e.g., Medical History, Reasons for Discontinuation from the Study, etc.), then only those categories for which there is at least 1 patient represented in 1 or more groups are included.
- An Unknown or Missing category is added to each parameter for which information is not available for 1 or more patients.
- Unless otherwise specified, the estimated mean and median for a set of values are printed out to 1 more significant digit than the original values, and standard deviations are printed out to 2 more significant digits than the original values. The minimum and maximum should report the same significant digits as the original values. For example, for systolic blood pressure:

N	XX
Mean	XXX.X
Std Dev	X.XX
Median	XXX.X
Minimum	XXX
Maximum	XXX

- P-values are output in the format: "0.xxx", where xxx is the value rounded to 3 decimal places. Every p-value less than 0.001 will be presented as <0.001. If the p-value are less than 0.0001, then present as <0.0001. If the p-value is returned as >0.999, then present as >0.999
- Percentage values are printed to one decimal place, in parentheses with no spaces, one space after the count (e.g., 7 (12.8%), 13 (5.4%)). Pre-determine how to display values that round down to 0.0. A common convention is to display as '<0.1', or as appropriate with additional decimal places. Unless otherwise noted, for all percentages, the number of patients in the analysis set for the treatment group who have an observation will be the denominator. Percentages after zero counts should not be displayed and percentages equating to 100% are presented as 100%, without decimal places.

This document is confidential.

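### The 100%-of-the-time sUA responder endpoint does not carry over the primary endpoint's failure rules, so some primary failures can leave its denominator or count as responders

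*SAP*

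**What the plan says.** SAP 9.3.3 lists the endpoint among the additional secondary endpoints. The plan is that the "percentage of patients who achieve and maintain reduction of sUA < 6 mg/dL for 100% of the time during TP6 will be provided" for the ITT set, followed by an MH comparison of each SEL-212 arm with placebo, stratified by tophus presence, with a 95% interval. Protocol 13.4.3 makes such p-values exploratory and leaves details to the SAP. Neither text mentions failure rules or missing data for this endpoint.

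The rules that could apply are limited elsewhere:

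- SAP Section 6 is titled "Estimands for Primary and Key Secondary Efficacy Endpoints". Its main primary estimand in 6.1 states: "Meeting the pre-defined treatment stopping criteria is considered as lack of efficacy and will be defined as treatment failures according to the composite strategy". Stopping for an adverse event, stopping for severe or critical COVID-19, death and sUA-lowering prohibited medication are handled in the same way.
- SAP 9.2, for the primary: "For missing response evaluation data in TP6 (see also Section 9.1) values will be multiple imputed".
- SAP 7.3: "Missing data will be imputed for the primary efficacy and key secondary efficacy variables as described in Section 9".
- SAP 14.2.5.2 sets the default, unless noted otherwise, that "for all percentages, the number of patients in the analysis set for the treatment group who have an observation will be the denominator".

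Where the authors want the primary's handling for another responder endpoint, they say so. SAP 6.2.5 ties the tophus-subset 80% endpoint to the 6.1 intercurrent-event list, and 9.3.2.5 applies the primary's analysis and restates the imputation model. SAP 9.3.3 has no such link.

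**The concern.** The 100% endpoint is the primary's Treatment Period 6 (TP6) curve with a stricter cut, so its responders should be a subset of the 80% responders, counted over the same patients. Two groups break that relation:

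- **Failures without an evaluable curve.** A patient who met a failure criterion and then left the study, or who died, is a non-responder under the main estimand. With no failure rule and no imputation, that patient has a missing 100% response and falls outside the default denominator.
- **Stopped patients back on urate-lowering therapy (ULT).** Protocol 7.4.1.1 permits return to ULT 60 days after the last dose. If sUA then stays below 6 mg/dL through TP6, the patient is a main-estimand failure but a responder here. This needs no dropout.

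The error leans toward SEL-212. The stopping rule requires sUA below 2.0 mg/dL one hour after the TP1 infusion. Saline patients who entered at 7 mg/dL or more will practically never meet that, so stopping-rule failures arise almost only on active drug. At stake is a pre-specified between-arm difference, interval and p-value that will be read beside the primary.

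**Working it through.** **Plan's own figure.** Inputs from SAP 3.5: 45% against 5%, two-sided alpha 2.5%, power 90%, continuity-corrected chi-square.

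- Uncorrected: n' = [2.2414·√(2·0.25·0.75) + 1.2816·√(0.45·0.55 + 0.05·0.95)]² / 0.40² = 26.7, so 27.
- Corrected: n = (n'/4)·[1 + √(1 + 4/(n'·0.40))]² = 31.5, so 32.
- With 8% early termination: 32/0.92 = 34.8, so 35 per arm and 105 in total. The SAP's 32, 35 and 105 are reproduced.

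The documents give no figure for the 100% endpoint, so what follows is denominator arithmetic for one SEL-212 arm of 40 with 18 primary responders (45%).

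**Attrition.** SAP 3.5 assumes about 8% early termination: 0.08 × 40 = 3.2. Protocol 7.6.3.2.2 reports 22/170 = 12.9% discontinued: 0.129 × 40 = 5.2. That gives 3 to 5 leavers. How many are failures, and how many of the 18 responders miss the 100% bar, are assumptions.

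**Case A: two leavers have no failure event and k are failures; 16 patients meet the 100% bar.** As written, the rate is 16/(40 − 2 − k). Under the main-estimand rules the k failures stay as non-responders, and the two others, missing at random, leave the expected rate at 16/38 = 42.1%. The 80% rate on the same basis is 18/38 = 47.4%.

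| k | Leavers | As written | Main rules | Inflation |
|---|---|---|---|---|
| 1 | 3 | 16/37 = 43.2% | 42.1% | 1.1 points |
| 2 | 4 | 16/36 = 44.4% | 42.1% | 2.3 points |
| 3 | 5 | 16/35 = 45.7% | 42.1% | 3.6 points |

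All three stay below 47.4%. At k = 4 the rate is 16/34 = 47.1%, still below. It passes the 80% rate only at k = 5 (16/33 = 48.5%), which means 7 of 40 missing, or 17.5%.

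**Case B: every leaver is a failure.** Let m be the leavers and x the primary responders who miss the 100% bar. As written the rate is (18 − x)/(40 − m); under the main rules it is (18 − x)/40. The former exceeds 18/40 when x < 0.45m.

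| m | x | As written | Main rules | Inflation | Above 45.0%? |
|---|---|---|---|---|---|
| 3 | 1 | 17/37 = 45.9% | 42.5% | 3.4 points | Yes |
| 3 | 2 | 16/37 = 43.2% | 40.0% | 3.2 points | No |
| 5 | 0 | 18/35 = 51.4% | 45.0% | 6.4 points | Yes |
| 5 | 2 | 16/35 = 45.7% | 40.0% | 5.7 points | Yes |

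With placebo at 2/40, the difference from placebo is 40.9 instead of 37.5 points (m = 3, x = 1), or 40.7 instead of 35.0 (m = 5, x = 2). Losing three non-responders from placebo as well would move 5.0% only to 2/37 = 5.4%.

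**ULT timing.** The TPk dose falls on about Day 28(k − 1). Adding 60 days gives Day 60, 88 and 116 for a last dose in TP1, TP2 or TP3, all before TP6 opens at about Day 140. A last dose in TP4 gives Day 144, already inside TP6.

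**The case against.** The SAP is silent on this endpoint; it does not direct that failures be excluded. The denominator rule is a general table convention that yields where something else is noted. The next bullets of SAP 14.2.5.2 ask for care in choosing denominators, and 9.3.3 names the ITT population. This limits how firmly the exclusion can be asserted, but not the need for a rule. Naming ITT does not settle the matter, because the convention operates within the analysis set, and nothing else tells the programmer what to do.

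Several stronger conclusions that a reader might draw are not supported:

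- **That stopped patients in general vanish from the table.** Patients withdrawn from drug continue visits to the end of TP12 (SAP 3.3). Under SAP 9.1 the response is missing only with two or fewer assessments less than 7 days apart. A stopped patient who attends is observed, usually as a non-responder.
- **That the inflation is large.** Eight failures leaving, on top of two other missing patients, gives 16/30 = 53.3%, about 11 points too high, but requires 10 of 40 missing. The 12.9% is itself all-cause discontinuation across both arms of an open-label study, not a rate among stopped SEL-212 patients.
- **That the missing imputation matters in its own right.** The 9.2 model uses only tophus status and treatment, and the MH analysis already stratifies by tophus. For patients missing without a failure event, observed-case and imputed estimates nearly agree. The failure rule is what counts.
- **That no 80% table can be read beside this one.** SAP 9.1 plans an ITT table of 80% responders from the same observed curve. The 100% responders are nested in it. The mismatch is with the main-estimand table of 9.2.

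The ULT route is probably rare. Most of the population failed xanthine oxidase inhibitors or cannot take them, and Protocol 10.5 keeps participants off ULT, which needs reconciling with 7.4.1.1. The second primary estimand also counts observed sUA regardless of ULT, so that handling is defensible if chosen, but here it is not stated.

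**Conclusion.** The point holds as an unhandled gap with a small, directional effect. As written, main-estimand failures without an evaluable TP6 curve are excluded by default, and a stopped patient controlled on ULT can count as a responder. Both errors tend to favour SEL-212.

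The likely inflation of a SEL-212 rate is about 1 to 4 points, if attrition is 8 to 13% and two leavers per arm had no failure event. It is about 3 to 6 points if every leaver is a failure. The ULT route is not quantified.

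A reader might infer that the stricter endpoint will overtake the primary. It could do so only if most leavers are failures and few responders miss the 100% bar (x < 0.45m in Case B). In Case A it does not happen at the documents' attrition.

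The endpoint is outside the testing hierarchy, so type I error for the primary and key secondary tests is untouched.

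**What to change.** Add to SAP 9.3.3 that the 100% endpoint uses the main-estimand intercurrent-event handling of Section 6.1 on all ITT patients, so that any main-estimand failure is a non-responder, and that remaining missing responses are multiply imputed as in Section 9.2. Add a matching clause to SAP 7.3, which now limits imputation to the primary and key secondary variables. Protocol 13.4.3 leaves these details to the SAP, so its text can stand.

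Forcing 100% responders to be 80% responders within each imputed dataset is optional. It needs the two responses to be imputed together, which is more than reuse of the primary program, and it affects only the few patients who are missing without a failure event.

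The cost is a sentence or two in the SAP and modest programming. The downside is a slightly less favourable reported SEL-212 rate.
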